#### 4.6.1 Justification for Pembrolizumab Dose

The planned dose of pembrolizumab for this study is 200 mg every 3 weeks (Q3W). Based on the totality of data generated in the Keytruda development program, 200 mg Q3W is the appropriate dose of pembrolizumab for adults across all indications and regardless of tumor type. As outlined below, this dose is justified by:

- Clinical data from 8 randomized studies demonstrating flat dose- and exposure-efficacy relationships from 2 mg/kg Q3W to 10 mg/kg every 2 weeks (Q2W),
- Clinical data showing meaningful improvement in benefit-risk including overall survival at 200 mg Q3W across multiple indications, and
- Pharmacology data showing full target saturation in both systemic circulation (inferred from pharmacokinetic [PK] data) and tumor (inferred from physiologically-based PK [PBPK] analysis) at 200 mg Q3W

Among the 8 randomized dose-comparison studies, a total of 2262 participants were enrolled with melanoma and non-small cell lung cancer (NSCLC), covering different disease settings (treatment naïve, previously treated, PD-L1 enriched, and all-comers) and different treatment settings (monotherapy and in combination with chemotherapy). Five studies compared 2 mg/kg Q3W versus 10 mg/kg Q2W (KN001 Cohort B2, KN001 Cohort D, KN002, KN010, and KN021), and 3 studies compared 10 mg/kg Q3W versus 10 mg/kg Q2W (KN001 Cohort B3, KN001 Cohort F2 and KN006). These studies demonstrated flat dose- and exposure-response relationships across the doses studied representing an approximate 5- to 7.5-fold difference in exposure. The 2 mg/kg (or 200 mg fixed-dose) Q3W provided similar responses to the highest doses studied. Subsequently, flat dose-exposure-response relationships were also observed in other tumor types including head and neck cancer, bladder cancer, gastric cancer and classical Hodgkin Lymphoma, confirming 200 mg Q3W as the appropriate dose independent of the tumor type. These findings are consistent with the mechanism of action of pembrolizumab, which acts by interaction with immune cells, and not via direct binding to cancer cells.

Additionally, pharmacology data clearly show target saturation at 200 mg Q3W. First, PK data in KN001 evaluating target-mediated drug disposition (TMDD) conclusively demonstrated saturation of PD-1 in systemic circulation at doses much lower than 200 mg Q3W. Second, a PBPK analysis was conducted to predict tumor PD-1 saturation over a wide range of tumor penetration and PD-1 expression. This evaluation concluded that pembrolizumab at 200 mg Q3W achieves full PD-1 saturation in both blood and tumor.

Finally, population PK analysis of pembrolizumab, which characterized the influence of body weight and other participant covariates on exposure, has shown that the fixed-dosing provides similar control of PK variability as weight-based dosing, with considerable overlap in the distribution of exposures from the 200 mg Q3W fixed dose and 2 mg/kg Q3W dose. Supported by these PK characteristics and given that fixed-dose has advantages of reduced dosing complexity and reduced potential of dosing errors, the 200 mg Q3W fixed-dose was selected for evaluation across all pembrolizumab protocols.

## 4.6.2 Rationale for Endpoints

### 4.6.2.1 Efficacy Endpoints

- Progression-free survival duration following study enrollment (primary endpoint).
  - Progression-free survival is a standard assessment of clinical benefit of treatments for locally advanced NSCLC.
- Duration of freedom from distant metastasis following study enrollment.
  - Freedom from distant metastasis is a standard assessment for patients with locally advanced NSCLC, who are at high risk of developing metastatic disease.
- Duration of freedom from intrathoracic disease progression following study enrollment.

- Freedom from intrathoracic disease progression is a standard assessment for patients with locally advanced NSCLC, who are at high risk of developing local/regional disease progression.
- Survival duration following study enrollment.
  - Overall survival is a standard assessment of clinical benefit of treatments for NSCLC.
- Disease progression during induction pembrolizumab for patients with PD-L1 expression  $\geq 50\%$ .
  - As induction pembrolizumab prior to radiotherapy for locally advanced NSCLC is a novel treatment approach, it will be important to characterize the rate of disease progression during induction therapy.

#### **4.6.2.2 Safety Endpoints**

- Severe (grade  $\geq 3$ ) adverse events, scored using CTCAE v 4.03.
  - It will be important to characterize the toxicity profile of sequential pembrolizumab and radiotherapy for locally advanced NSCLC, as this is a novel treatment approach.
- Pneumonitis (grade  $\geq 2$ ).
  - It will be important to characterize the rate of pneumonitis, which may occur because of radiotherapy or immunotherapy, for study subjects.
- Patient-reported treatment-related toxicity, scored using PRO-CTCAE.
  - See Section 4.5
- Unplanned hospitalization.
  - Many patients treated with radiotherapy or chemoradiotherapy for locally advanced NSCLC are hospitalized due to treatment toxicity. It will be important to characterize the hospitalization rate for patients treated with pembrolizumab and radiotherapy for locally advanced NSCLC.
- Daily step counts, measured using wearable fitness trackers.
  - See Section 4.4

#### **4.6.2.3 Translational Endpoints**

- Clearance of circulating tumor DNA following radiotherapy.

- Subjects in the PembroRT and ChemoRT cohorts will undergo circulating tumor DNA testing at study entry and several weeks after the completion of thoracic radiotherapy. Circulating tumor DNA clearance may be a powerful predictor of disease control following conventional treatment for locally advanced NSCLC[39]. We will test the prognostic utility of circulating tumor DNA testing for patients treated with pembrolizumab and radiotherapy and compare rates of circulating tumor DNA clearance in the two study cohorts.
- PD-L1 TPS score and expression of alternate immune checkpoint molecules.
  - Tumor PD-L1 expression as determined by immunohistochemistry (IHC) has been implicated as a predictive biomarker for benefit from treatment with PD-1/PD-L1 inhibitors[40, 41]. We will assess baseline PD-L1 expression for each study subject using our in-house and FDA-approved immunohistochemical assay on archival FFPE tumor tissue. Sections cut from FFPE blocks will be deparaffinized and subjected to heat-induced epitope retrieval. Slides will be incubated with the primary antibody (monoclonal mouse anti-PD-L1, clone 22C3) and visualized using the EnVision FLEX system on the Dako Autostainer Link 48. Protein expression will be quantified as tumor proportion score (TPS), which is the percentage of tumor cells demonstrating PD-L1 membrane staining. Subjects will be assigned to the PembroRT or ChemoRT cohort based on PD-L1 expression, using a cutoff of 50%. Within each cohort, we will explore if PD-L1 expression level is associated with clinical outcomes, including progression-free survival and overall survival.
  - We will also quantify baseline tumor expression of alternate immune checkpoint molecules in peripheral blood as well as from fresh tumor material (if available). From blood samples, peripheral blood mononuclear cells will be isolated using Ficoll Paque density gradient centrifugation, followed by antibody labeling and analysis. From biopsy specimens, tumor will be dissociated without enzymatic digestion, followed by antibody labeling for multi-color flow cytometric analysis that will focus on expression of HHLA2, PD-L1, PD-L2, B7-H3, and B7x (B7-H4/B7S1) in CD8-positive T cells and regulatory cells. We will explore if expression of immune checkpoint molecules is associated with clinical outcomes.
- Tumor mutational burden.
  - Tumor mutational burden has been identified as a predictive factor for response to immune checkpoint blockade in several settings[42-44]. We will utilize a validated commercial platform to explore tumor mutational burden as a prognostic factor for study subjects.
- Markers of immune activation.
  - The PD-1 receptor and its ligands define a novel regulatory pathway with potential inhibitory effects on T, B, and monocyte responses[41, 45]. We will characterize how study therapy affects several markers of immune activation

throughout the treatment course. Blood collected from study subjects will be centrifuged to isolate peripheral blood mononuclear cells, and flow cytometry will be performed for immunophenotyping of mononuclear cells using several panels to quantify populations of B cells, CD4 and CD8 cells, natural killer cells, monocytes, and myeloid and plasmacytoid dendritic cells. CD4, CD8, and regulatory T cell populations will be tested for markers of activation, including expression of PD-1, ICOS, and CTLA-4. We may identify predictors of long-term clinical outcomes. Additionally, we may identify bottlenecks where treatment resistance may be overcome by the addition of additional immunomodulatory agents in the future.

## 5.0 METHODOLOGY

### 5.1 Study Population

#### 5.1.1 Participant Inclusion Criteria

Participants are eligible to be included in the study only if all the following criteria apply:

1. Male/female participants who are at least 18 years of age on the day of signing informed consent with histologically confirmed diagnosis of non-small cell lung cancer will be enrolled in this study.
2. Previously untreated, pathologically proven NSCLC with measurable disease (at least 1 unidimensional, radiographically measurable lesion based on RECIST v1.1) and one of the following stages: (prior resection for early stage disease is allowed)
  - a. AJCC version 8 Stage II disease, medically or technically unresectable
  - b. AJCC version 8 Stage III disease
3. Whole body PET/CT within 42 days prior to study entry demonstrating hypermetabolic pulmonary lesion(s) and/or thoracic lymph node(s). If PET/CT was obtained more than 42 days prior to study entry and is not repeated, CT within 28 days prior to study entry demonstrating no evidence of metastatic disease is required.
4. MRI of the brain or head CT with contrast within 42 days prior to study entry.
5. PFTs within 42 days of study entry
6. ECOG performance status 0-1
7. Adequate end-organ function, based on routine clinical and laboratory workup:
  - a. ANC >1,500 cells/ $\mu$ l, Platelets  $\geq$  100,000 cells/ $\mu$ l, Hemoglobin  $\geq$  9.0 g/dl
  - b. Serum creatinine  $\leq$  1.5 x ULN or calculated creatinine clearance  $\geq$  50 ml/min
  - c. Total bilirubin  $\leq$  1.5 x ULN (or direct bilirubin below the ULN), AST and ALT  $\leq$  2.5 x ULN
  - d. International normalized ratio (INR) (or prothrombin time (PT)) and activated partial thromboplastin time (aPTT)  $\leq$  1.5 x ULN unless participant is receiving anticoagulant therapy, as long as values are within the intended therapeutic range

- e. Thyroid stimulating hormone (TSH) within normal limits. If TSH is not within normal limits, the participant may be eligible if T3 and free T4 are within normal limits.
8. A female participant is eligible to participate if she is not pregnant (see Exclusion Criteria), not breastfeeding, and at least one of the following conditions applies:
  - a. Not a woman of childbearing potential (WOCBP) as defined in the Appendix
  - b. A WOCBP who agrees to follow the contraceptive guidance in the Appendix during the treatment period and for at least 120 days after the last dose of study treatment with pembrolizumab (pembroRT cohort) or at least 180 days after the last dose of chemotherapy (chemoRT cohort).
9. A male participant must agree to use contraception during the treatment period and for at least 28 days after the last dose of study treatment and refrain from donating sperm during this period.
10. The participant (or legally acceptable representative if applicable) provides written informed consent for the trial.

### **5.1.2 Participant Exclusion Criteria**

Participants are excluded from the study if any of the following criteria apply:

1. Malignant pleural or pericardial effusion, based on clinical, imaging, or pathologic evaluation.
2. Systemic therapy for lung cancer within the past year.
3. Prior therapy with an anti-PD-1, anti-PD-L1, or anti-PD-L2 agent or with an agent directed to another stimulatory or co-inhibitory T-cell receptor (e.g., CTLA-4, OX-40, CD137).
4. Contraindication to protocol-specified radiotherapy, such as prior thoracic radiotherapy or active serious collagen vascular disease (e.g. scleroderma).
5. Is currently participating in or has participated in a study of an investigational agent or has used an investigational device within 4 weeks prior to the first dose of study treatment.
6. Active malignancy other than lung cancer that requires active treatment other than hormonal therapy or is deemed by the treating physicians to be likely to affect the subject's survival duration.
7. A history of (non-infectious) pneumonitis that required steroids or current pneumonitis.
8. Active infection requiring antimicrobial therapy.

9. Has a known history of active TB (Bacillus Tuberculosis).
10. Has a history or current evidence of any condition, therapy, or laboratory abnormality that might confound the results of the study, interfere with the subject's participation for the full duration of the study, or is not in the best interest of the subject to participate, in the opinion of the treating investigator.
11. Has known psychiatric or substance abuse disorders that would interfere with cooperation with the requirements of the trial.
12. Pregnancy, assessed in WOCBP (defined in Appendix) with urine pregnancy test within 72 hours prior to study treatment allocation. If urine pregnancy test is positive or cannot be confirmed as negative, a serum pregnancy test is required. If more than 72 hours elapse between screening pregnancy test and the first dose of study treatment, another pregnancy test (urine or serum) must be performed and must be negative.
13. For patients receiving pembrolizumab/radiotherapy
  - a. Has severe hypersensitivity ( $\geq$ Grade 3) to pembrolizumab and/or any of its excipients.
  - b. Active autoimmune disease other than vitiligo, thyroid disorders, Sjogren's disease, and well-controlled rheumatoid arthritis not requiring disease-modifying therapy.
  - c. Has received a live vaccine within 30 days prior to the first dose of study drug. Examples of live vaccines include, but are not limited to, the following: measles, mumps, rubella, varicella/zoster (chicken pox), yellow fever, rabies, Bacillus Calmette–Guérin (BCG), and typhoid vaccine. Seasonal influenza vaccines for injection are generally killed virus vaccines and are allowed; however, intranasal influenza vaccines (e.g., FluMist®) are live attenuated vaccines and are not allowed.
  - d. Has a diagnosis of immunodeficiency or is receiving chronic systemic steroid therapy (in dosing exceeding 10 mg daily of prednisone equivalent) or any other form of immunosuppressive therapy within 7 days prior to the first dose of study drug.

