#### **5.2.2 Chemotherapy (ChemoRT Cohort Only)**

Chemotherapy will be administered weekly during radiotherapy. This concurrent chemotherapy will consist of carboplatin (AUC 2, IV) and paclitaxel (50 mg/m^2, IV). Standard institutional procedures will be used for chemotherapy formulation, calculation of AUC, and chemotherapy administration. Treating physicians may implement dose reductions or withhold chemotherapy in the event of adverse events or laboratory abnormalities, per usual care.

Adjuvant systemic therapy may be administered for patients on the ChemoRT cohort, at the discretion of the treating physicians. In some cases, this may consist of adjuvant systemic doses of chemotherapy (e.g.: carboplatin AUC 6 and paclitaxel 200 mg/m^2). Based on emerging data[10], patients on the ChemoRT cohort may be treated with adjuvant immunotherapy.

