### 8.2 Statistical Analysis Plan – Secondary Endpoints

Time-to-event outcomes (overall survival, freedom from distant metastasis, freedom from intrathoracic progression, freedom from hospitalization) will be analyzed using the Kaplan-Meier method, from which rates at various time points and corresponding 95% confidence intervals will be estimated. Exploratory comparisons for time-to-event outcomes between the PembroRT and ChemoRT cohorts will be performed using log-rank tests. Univariate and

multivariable Cox regression models will be used to evaluate associations between time-to-event outcomes and clinical covariates, including study cohort.

Rates of radiographic responses and disease progression during induction pembrolizumab for subjects in the PembroRT cohort will be described using counts and percentages. Logistic regression models will be used to evaluate potential predictors of response or progression (e.g.: PD-L1 TPS).

Hospitalization rates and adverse event rates, scored using CTCAE as well as PRO-CTCAE, will be presented as counts and percentages. Exploratory comparisons between the PembroRT cohort and the ChemoRT cohort will be performed using chi-square or Fisher Exact testing, as appropriate.

Daily step counts throughout the study period will be presented using descriptive statistics and will be analyzed using a generalized linear mixed-model for repeated measures.

Rates of circulating tumor DNA clearance will be presented as counts and percentages, and predictors of circulating tumor DNA clearance will be explored using chi-square or Fisher exact testing, as appropriate. Exploratory analyses will be performed to evaluate PD-L1 expression, expression of alternative immune checkpoint molecules (e.g., HHLA2, B7x, and B7-H3), baseline tumor mutational burden, and markers of immune activation (e.g., expansion of T4/T8 subsets, myeloid derived suppressor cell levels, expansion of T-cell repertoire) as predictors of PFS and overall survival.

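### Exclusions 13b and 13d apply to PembroRT only, so the unadjusted between-cohort safety comparisons carry an avoidable eligibility difference that no stated caveat covers

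*Combined protocol and SAP*

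**What the plan says.** Section 5.3 assigns the cohort by PD-L1 tumor proportion score alone, with the cut at 50%. Most entry criteria in sections 5.1.1 and 5.1.2 are common to both cohorts, including "ECOG performance status 0-1" and "Adequate end-organ function, based on routine clinical and laboratory workup".

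Exclusion 13 is different. It is introduced by "For patients receiving pembrolizumab/radiotherapy" and has four items. Item 13b is "Active autoimmune disease other than vitiligo, thyroid disorders, Sjogren's disease, and well-controlled rheumatoid arthritis not requiring disease-modifying therapy". Item 13d begins "Has a diagnosis of immunodeficiency or is receiving chronic systemic steroid therapy" (above 10 mg prednisone equivalent daily) and extends to any other immunosuppressive therapy within 7 days before the first dose. Items 13a (hypersensitivity to pembrolizumab) and 13c (recent live vaccine) have little bearing on the outcomes compared.

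Section 5.4.2 prohibits most systemic glucocorticoid use during screening and treatment and does not limit this to one cohort, although the live-vaccine bullet in the same list is limited to PembroRT.

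For adverse events (CTCAE and PRO-CTCAE) and hospitalization rates, section 8.2 states: "Exploratory comparisons between the PembroRT cohort and the ChemoRT cohort will be performed using chi-square or Fisher Exact testing, as appropriate". Time-to-event outcomes get log-rank tests and Cox models, including multivariable ones, whose covariates are not listed apart from cohort. Section 8.2 defines no analysis set for these comparisons, so everyone enrolled in each cohort is the natural reading. Section 4.6 and objectives 5 to 9 acknowledge the lack of randomization, and section 4.6 offers institutional data that PD-L1 is not prognostic.

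**The concern.** Take two patients with the same active autoimmune disease, both otherwise eligible. With a score of 49%, the patient enters ChemoRT. With a score of 50%, the patient is turned away and is not moved to the other cohort. The cohorts therefore differ by entry rule as well as by PD-L1 and treatment.

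The data in section 4.6 cannot answer this. Even if PD-L1 were wholly unrelated to outcome, ChemoRT could still contain patients with immune conditions who are absent from PembroRT by design. PD-L1 confounding is built into the trial; this difference can be removed at analysis.

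Objectives 5 to 9 are at stake. They set out to demonstrate fewer severe adverse events, no significant increase in pneumonitis, less patient-reported toxicity, preserved step counts and fewer hospitalizations with PembroRT. If patients with 13b or 13d conditions have more severe events or admissions, part of any observed advantage would come from eligibility. That direction is a plausible judgement, not a documented fact.

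**Working it through.** **Cohort sizes (section 8.1).** With 25 PembroRT patients and 40% of patients at 50% or higher: 25 / 0.40 = 62.5 in total, and 62.5 − 25 = 37.5 in ChemoRT. These round to the plan's 63 and 38.

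**What is not touched.** The primary test sets PembroRT against a fixed one-year PFS rate of 40%. Secondary objectives 1 to 3 refer to historical outcomes and objective 4 to PembroRT alone. None uses ChemoRT data.

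**How far other rules close the gap.**
- Exclusion 4 covers only contraindications to radiotherapy, such as active serious collagen vascular disease.
- Exclusion 7 covers pneumonitis, and exclusion 8 active infection.
- Exclusion 10 covers confounding conditions, but rests on investigator opinion.
- Section 5.4.2, as written, would remove most steroid users from ChemoRT as well.

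What remains is other active autoimmune disease, immunodeficiency and non-steroid immunosuppression.

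**Size of the shift with no true cohort difference.** The documents give neither the share q of ChemoRT patients with a 13b or 13d condition nor their excess risk. All values below are assumptions.

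*Relative form:* shift = q × p × (RR − 1), with p the base rate of severe events.
- Smallest: q = 0.03 (1.1 of 38 patients), p = 0.30, RR = 1.25: 0.03 × 0.30 × 0.25 = 0.2 points.
- Largest at p = 0.30: q = 0.15 (5.7 of 38), RR = 2: 0.15 × 0.30 × 1 = 4.5 points.
- Largest at p = 0.50: q = 0.15, RR = 2: 0.15 × 0.50 × 1 = 7.5 points.

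*Absolute form:* shift = q × d, with d the excess risk.
- q = 0.05 (1.9 of 38), d = 0.20: 1 point.
- q = 0.10 (3.8 of 38), d = 0.30: 3 points.
- q = 0.20 (7.6 of 38), d = 0.40: 8 points.

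**Against sampling error.** The 95% half-width for a difference in rates is 1.96 × √[p(1 − p)(1/25 + 1/38)].
- p = 0.30: 1.96 × √(0.21 × 0.0663) = 23 points.
- p = 0.50: 1.96 × √(0.25 × 0.0663) = 25 points.

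**Effect on the test.** Over the relative-form range, the chance of a significant result favouring PembroRT when there is no real difference rises from the nominal 2.5% to between 2.6% and 8.4% (normal approximation).

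**Time-to-event outcomes.** If the affected patients have hazard h times that of the others, the spurious hazard ratio is roughly 1 / (1 − q + q × h). For q = 0.05, h = 1.25 this is 1/1.0125 = 0.99; for q = 0.15, h = 2 it is 1/1.15 = 0.87.

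**The case against.** The strongest reply is that the comparisons are already labelled exploratory, the objectives carry a non-randomization caveat, and section 4.6 presents ChemoRT only as a point of reference. Any shift is also small beside the sampling error. This limits the weight of the point but does not answer it. The caveats never mention unequal entry rules, the objectives are still worded as demonstrations, and a wide interval reflects random error without removing a systematic shift.

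Three stronger readings are tempting, and the documents support none of them.
- A reader might infer that ChemoRT admits frailer patients. The criteria that measure fitness, performance status and organ function, are common to both cohorts. Items 13b and 13d identify immune conditions, and nothing in the documents says such patients tolerate chemoradiotherapy worse.
- A reader might infer that every between-cohort comparison is tilted toward PembroRT. No prevalence or excess risk is given, and no link to circulating tumor DNA clearance or step counts is documented. Time-to-event outcomes have planned, if unspecified, multivariable adjustment.
- A reader might infer that the affected ChemoRT patients would seldom receive adjuvant immunotherapy, worsening their survival outcomes. Section 5.2.2 says only that "patients on the ChemoRT cohort may be treated with adjuvant immunotherapy", with adjuvant therapy left to physician discretion. If use were lower, the effect could even reverse for pneumonitis, which section 4.6.2.2 attributes to radiotherapy or immunotherapy: less immunotherapy could mean less pneumonitis in ChemoRT.

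**Conclusion.** The asymmetry is plain in the text, and section 8.2 does not deal with it. It bears mainly on the unadjusted comparisons of severe adverse events, pneumonitis, PRO-CTCAE toxicity and hospitalization. For severe adverse events and hospitalization the likely direction is toward PembroRT; for pneumonitis it is unclear. The shift is under 1 to about 8 points, wholly dependent on assumed shares of 3 to 20% and assumed excess risks. That is too little to explain a large difference, but enough to affect a borderline one.

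The point is secondary to the complete confounding of cohort with PD-L1, which no analysis here can remove. It is worth acting on because it is avoidable and cheap to fix, and a restricted comparison chosen after outcomes are known would carry little credibility.

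**What to change.** 1. Record 13b and 13d status at baseline for every ChemoRT patient. The sources exist: the signed eligibility checklist (section 5.7), medical history with active conditions (section 7.1.1.3) and medications from 28 days before the first dose (section 5.4.1), which spans the 7-day window in 13d.
2. State in section 8.2 that each PembroRT-versus-ChemoRT comparison is reported twice: with all enrolled patients, and with ChemoRT restricted to those who would have passed 13b and 13d. Require any claim under objectives 5 to 9 to hold in the restricted set.
3. Name the eligibility difference beside the existing non-randomization caveat.
4. Reconcile the scope of 13d (PembroRT only) with the glucocorticoid prohibition in section 5.4.2 (no cohort limit), so that it is clear which ChemoRT patients the restriction removes.

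ChemoRT enrolment and the primary analysis do not change. The cost is one checklist section, a few sentences and a little precision. If 6 of 38 patients drop out, the half-width at p = 0.50 becomes 1.96 × √[0.25 × (1/25 + 1/32)] = 26.2 points instead of 25.2; if 8 drop out, 1.96 × √[0.25 × (1/25 + 1/30)] = 26.5 points.
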